4.2.1 Group A – main study

All patients with AKI will be screened for inclusion into the study, as well as those patients tested for possible AKI but who did not sustain it. Patients will not be approached until at least two months after they have recovered from their acute illness, by which time the majority of patients will have returned home.

Recruitment, matching and consent

Patients who meet the inclusion criteria will be contacted via post and invited to participate. The control group will be matched to AKI patients on a 1:1 basis in terms of baseline eGFR (within the same CKD stage but as closely as possible) and age \pm 5yrs. In addition they will be recruited from a similar inpatient setting. Due to the proposed three year follow up, patients over 85yrs will be excluded as the reduced life expectancy due to age alone in these patients may affect the outcome measures of mortality.

Potential subjects will receive a letter of invitation along with a comprehensive patient information sheet. Interested patients will be asked to telephone a number at the Royal Derby Hospital during which patient identity will be affirmed using standard data protection questions. After confirmation that the patients are in possession of the information required to provide valid consent, they will be sent a consent form that they will sign and return in a pre-paid envelope, retaining a copy for themselves (see section 4.2.2 for more details of the consent process). If patients do not wish to participate they will be asked to confirm this by telephoning the same number. This methodology has been piloted and has been shown to be very successful in more than 300 patients to date, with very positive feedback from participants.

Each patient will be assigned a unique study number that will be used to identify all data collected for the study. This will be allocated upon recruitment. A key of patient identity and study numbers will be kept on a password-protected Trust server in a password-protected file. Any information passed onto the Medical Research Information Service will be in encrypted form. A recruitment log will be maintained and the patients' GPs will be informed of their participation in the study by letter.

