8.1 Sample Size Determination

The original sample size for the study was based on some assumptions and information published in two studies [10, 11] so in line with the statistical plan in version 1.2 of the protocol, the sample size calculation has been repeated using one year results from the pilot study. The new sample size calculation is based on percentage change in eGFR at one year, a surrogate for subsequent CKD progression (doubling of serum creatinine or progression to CKD stage 5/dialysis). A previous study reported that 21.4% of those who experienced a 20% fall in eGFR at one year progressed to initiation of RRT [18]. Results from the pilot study have shown that 13 patients experienced such a decline in eGFR at one year in the control group as compared to 29 in the AKI group. Therefore, the estimated proportion in the control group that will progress to a doubling of serum creatinine or progression to CKD stage 5 is 2.02% as compared to 4.41% of the AKI group. Assuming a 5% significance level and 80% power this means that 430 patients will be required per group. Assuming a drop-out rate of 26% then a total of 542 patients will be required in each group.

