8.2 Statistical Methods

Statistical analysis will be performed using SPSS v19.0 and Stata v11. Descriptive statistics will be used to summarise baseline variables in AKI and control groups. Univariate parametric or non-parametric analysis will be done to compare the two groups at baseline. Kaplan-Meier curves will be constructed to compare the primary endpoints, renal end-point and mortality between the two groups using the Log-Rank test. A Cox proportional hazard model will be used to test the effect of AKI on primary endpoints adjusted for age, gender, (race if possible), co-morbidity (diabetes, hypertension, malignancy, cardiovascular disease), baseline renal function, proteinuria, requirement for acute dialysis and multiple episodes of AKI. Conditional logistic regression will be performed for exploring the effect of AKI matched patients and secondary outcomes on the proportion of patients with CKD progression and on their mortality status at 12 months. Participants with cirrhosis will be included in the main analysis, but their co-morbid conditions will be accounted for in the statistical analysis.

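### For mortality, the plain log-rank test in section 8.2 ignores the 1:1 matching and is conservative; stratifying it by age band and CKD stage recovers power at no cost

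*Protocol*

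**What the plan says.** Section 4.2.1 sets the matching: "The control group will be matched to AKI patients on a 1:1 basis in terms of baseline eGFR". The match is within the same CKD stage and as close as possible, with age within 5 years and recruitment from a similar inpatient setting. Section 4.2.3 repeats this for the liver group.

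Section 8.2 then names the unadjusted comparison for death and the renal endpoint: "Kaplan-Meier curves will be constructed to compare the primary endpoints, renal end-point and mortality between the two groups using the Log-Rank test". It mentions no strata and no pairing.

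Two other analyses in 8.2 do touch the matching factors. The first is the Cox model: "A Cox proportional hazard model will be used to test the effect of AKI on primary endpoints adjusted for age, gender". Its covariates also include co-morbidity, baseline renal function, proteinuria, acute dialysis and multiple AKI episodes. The second is explicitly matched: "Conditional logistic regression will be performed for exploring the effect of AKI matched patients". It covers the proportion with CKD progression and mortality status at 12 months. The wording leaves open whether the 12-month limit applies to both outcomes or to mortality only.

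**The concern.** The log-rank variance assumes that the two groups are independent. Here each control is chosen to resemble an AKI patient on factors that drive outcome. The protocol itself treats age as prognostic: section 4.2.1 excludes patients over 85 because age alone may affect mortality. Eligible ages run from 18 to 85, so age can separate pairs widely.

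If partners share risk, the difference between groups varies less than the formula assumes. The test then rejects too rarely, and precision gained by matching is thrown away. Mortality is where this should matter most, because deaths over ten years are likely to be common and related to age. The cost is a missed or imprecisely shown mortality difference. It is not a false positive.

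**Working it through.** **1. The plan's own power figure.** Section 8.1 states "Assuming a 5% significance level and 80% power this means that 430 patients will be required per group", for an estimated renal risk in controls that "is 2.02% as compared to 4.41% of the AKI group". The pooled two-sided formula is

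n = [1.96·√(2·p̄(1−p̄)) + 0.8416·√(p₁(1−p₁) + p₂(1−p₂))]² / (p₂−p₁)²

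With p₁ = 0.0202, p₂ = 0.0441 and p̄ = 0.03215:

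n = (0.4890 + 0.2095)² / 0.0239² ≈ 854 per group.

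The stated 430 is not reproduced; power at 430 per group is about 51%. That is a separate matter. It bears on this point only because the calculation allows nothing for matching, and because 430 per group implies 430 × (0.0202 + 0.0441) ≈ 28 renal events.

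**2. Direction and scale, analytically.** Let ρ be the within-pair correlation of the log-rank scores. The true variance is then (1−ρ) times the nominal one. For a test with nominal non-centrality δ = 1.96 + z(power):

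- true size = 2Φ(−1.96/√(1−ρ))
- power of the unpaired test = Φ((δ−1.96)/√(1−ρ))
- power of a test with the correct variance = Φ(δ/√(1−ρ) − 1.96)

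| ρ | True size | Unpaired vs correct, nominal power 50% | Unpaired vs correct, nominal power 80% |
|---|---|---|---|
| 0.05 | 4.4% | 50.0% vs 52.0% | 80.6% vs 82.0% |
| 0.10 | 3.9% | 50.0% vs 54.2% | 81.3% vs 84.0% |
| 0.184 | 3.0% | 50.0% vs 58.3% | 82.4% vs 87.3% |
| 0.29 | 2.0% | 50.0% vs 64.3% | 84.1% vs 91.4% |

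A size of 2-3% therefore needs ρ of about 0.18-0.29, which the protocol does not give. The loss is then 8-14 points for a test near 50% power, but only about 5-7 points near 80%.

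**3. Mortality, by simulation.** From the protocol: 430 pairs, partners within 5 years of age, 26% dropout (simulated as early censoring). Assumed: age SD 14 years, 30-45% deaths over ten years, hazard ratio 1.25, age log hazard ratio 0.4-0.8 per decade, SD of a shared inpatient-setting effect 0-0.5. There were 1,500 runs per cell. The comparator is a log-rank test stratified by 10-year age band.

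| Age effect per decade | Deaths | Size of plain log-rank | Power gained by stratifying |
|---|---|---|---|
| 0.6-0.8 | 30% | 2.9-4.2% | 7-14 points (28-35% to 39-46%) |
| 0.6-0.8 | 45% | 2.2-3.0% | 10-21 points |
| 0.4 | 30-45% | 2.7-4.9% | 2-5 points |

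A second simulation with 430 pairs, stratifying by age band and CKD stage, gave size 2.1-2.7% and a loss of 11-18 points for a strong age effect. For a weak one it gave size 4.4% and a loss of about 3 points. The stratified test held its size at 4.3-5.6% and cost no power.

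**4. Renal endpoint.** With 542 pairs, 26% early censoring, a control risk of 2.02% and a shared log-hazard SD of 0.5, 0.8, 1.0 and 1.3, the plain log-rank had size 4.8%, 4.9%, 4.5% and 4.3%. The power loss was 0-3 points. At 430 pairs, size was about 5% and power 54% with or without stratification. With so few events, pairs seldom both contribute, so the correlation has little effect.

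**5. Cox model adjusted for age and eGFR.** This used 542 pairs matched explicitly on both factors, under the null, with 1,500 runs.

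| Control mortality | Age log hazard ratio per decade | Log-rank size | Adjusted Cox size |
|---|---|---|---|
| 25% | 0.5 | 4.9% | 5.7% |
| 40% | 0.6 | 3.3% | 5.0% |
| 40% | 0.8 | 2.2% | 4.5% |
| 60% | 0.8 | 1.3% | 4.2% |

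The Monte Carlo standard error at 5% is √(0.05 × 0.95 / 1,500) ≈ 0.6 points, so the Cox sizes are compatible with nominal. For the renal endpoint the Cox size was about 3.4%, probably a small-sample effect of the Wald test with about 20 events.

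**6. How finely to stratify.** Adding inpatient setting as a third factor (six categories assumed) cut the mortality gain from about 9 points to about 5.5. It also lowered renal power by about 2 points (51% to 49%; 47% to 45% with stronger eGFR prognosis). Sections 4.2.1 and 4.2.3 define no categories for setting.

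**The case against.** The strongest reply is that the Cox model, not the log-rank test, carries the inference. The Study Summary and 8.2 both assign it to test the effect of AKI, and the Study Summary does not mention the log-rank test. The study is not randomised, so an adjusted analysis is the natural basis for a conclusion. A reader might infer that the Cox model also ignores the matching and has wrong standard errors. The protocol does not support that: age and baseline renal function are covariates, and step 5 shows near-nominal mortality size. Only residual pairing, such as inpatient setting, is left.

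This does not make the log-rank test irrelevant. The Cox model also adjusts for acute dialysis and multiple AKI episodes. Both arise essentially only in the AKI group, since 8.3 excludes controls who later sustain AKI. Its AKI coefficient is therefore not the overall AKI-versus-control contrast; the log-rank test supplies that contrast.

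Three further points stand in part:

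- **Conservative error.** The error cannot inflate false positives. That is correct; the harm is lost power.
- **Matching is used elsewhere.** The conditional logistic regression does use the pairs, but it is exploratory and, at least for mortality, stops at 12 months.
- **Strata are a matter for the SAP.** An SAP could add them. But 8.2 already names a specific test without them, so the sentence deserves correction where it stands.

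**Conclusion.** The point holds for the log-rank test on mortality. That test is conservative under this design. With 30-45% deaths and a hazard ratio of 1.25, it loses about 3 power points if age is weakly prognostic and roughly 7-18 if strongly, with the most extreme simulated cell at 21. True size under a strong age effect is about 2-4%. Mortality, hazard ratio and prognostic strength are all assumptions, so no single figure should be quoted as the trial's loss. A test already near 80% power would lose less.

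A reader might extend this to the renal endpoint, on which the study is sized. The protocol's own event rates do not support that: the loss there is 0-3 points and size stays near 5%. Nor does the point invalidate any analysis. It is a free improvement.

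**What to change.** In section 8.2, state that the log-rank comparison, at least for mortality, is stratified by 10-year age band and baseline CKD stage. State also that patients whose matched partner is lost or excluded stay in the analysis. Broad strata allow this; strict pair-by-pair stratification would discard information from broken pairs, including those that the control exclusion in 8.3 creates.

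Do not add inpatient setting as a stratum unless its categories are defined in advance and are not sparse. The Kaplan-Meier curves can stay as planned. Variance clustered on the matched pair is an optional refinement for the Cox model, to cover residual pairing.

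The cost is one or two sentences. Age and baseline renal function are already needed for matching, so no new data are required, and the stratified test showed no power cost in the simulations.

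### The renal Cox model fixed in section 8.2 has 11–12 coefficients but only about 2–3 expected events per coefficient at the planned rates; a penalised fit should be specified

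*Protocol*

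**What the plan says.** Section 3.2 names two primary endpoints: death and CKD progression. CKD progression is a composite of creatinine doubling, eGFR below 15 or the start of renal replacement therapy.

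For both endpoints section 8.2 fixes one adjusted model: "A Cox proportional hazard model will be used to test the effect of AKI on primary endpoints adjusted for age, gender, (race if possible"; the list continues with "co-morbidity (diabetes, hypertension, malignancy, cardiovascular disease), baseline renal function, proteinuria, requirement for acute dialysis and multiple episodes of AKI". Only race is conditional. The section adds that the co-morbid conditions of participants with cirrhosis will be accounted for, which could add terms. It does not tie the list to the number of events and provides for neither covariate reduction nor penalisation.

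Section 8.1 gives the rates on which the study is sized. The pilot found that "13 patients experienced such a decline in eGFR at one year in the control group as compared to 29 in the AKI group". A cited cohort is said to show that "21.4% of those who experienced a 20% fall in eGFR at one year progressed to initiation of RRT". The section concludes that the proportions expected to "progress to a doubling of serum creatinine or progression to CKD stage 5 is 2.02% as compared to 4.41% of the AKI group". It then states: "Assuming a 5% significance level and 80% power this means that 430 patients will be required per group", and: "Assuming a drop-out rate of 26% then a total of 542 patients will be required in each group". No expected number of renal events appears anywhere in the protocol.

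**The concern.** What a Cox model can support depends on its number of events, not its number of patients. A study of 1,084 people looks large enough for a dozen covariates, but with about 3% progressing the renal model has few events to work with. Several listed covariates are also likely to be sparse. Acute dialysis during AKI can occur only in the AKI group. Multiple AKI episodes are confined almost wholly to that group, because sections 4.3 and 8.3 exclude controls who later sustain AKI. If no carrier of such a covariate has a renal event, its maximum-likelihood coefficient is infinite and the fit may not converge.

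At stake is the adjusted AKI hazard ratio for one of the two primary endpoints, in an observational study where adjustment carries much of the argument.

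**Working it through.** **Inputs.** From section 8.1: control proportion p1 = 0.0202, AKI proportion p2 = 0.0441, 430 patients required and 542 recruited per group, 26% drop-out, 5% significance, 80% power. From section 8.2: the covariate list.

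**1. The plan's own figures.**
- The proportions follow from the pilot counts and the 21.4% conversion if the pilot groups had about 138 and 141 patients: 13 × 0.214 / 0.0202 = 137.7 and 29 × 0.214 / 0.0441 = 140.7. Section 8.1 does not state these denominators.
- The 430 is not reproduced. The two-proportion formula n = [z(0.975)·√(2p̄(1−p̄)) + z(0.80)·√(p1(1−p1) + p2(1−p2))]² / (p2−p1)², with p̄ = 0.03215, gives 854 per group (673 one-sided).
- The 542 is 430 × 1.26 = 541.8; dividing by 1 − 0.26 gives 582.

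These are separate matters. The stated 430 and 542 are used below because they are what the study plans to have.

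**2. Coefficients.** AKI (1) + age, gender, race (3) + four co-morbidities (4) + baseline renal function, proteinuria, acute dialysis, multiple episodes (4) = 12, or 11 without race. A race variable with several categories would add more.

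**3. Expected events.** Events = n per group × (0.0202 + 0.0441).

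| n per group | Basis | Control | AKI | Total | Per coefficient (12) | Per coefficient (11) |
|---|---|---|---|---|---|---|
| 401 | 542 × 0.74 | 8.1 | 17.7 | 25.8 | 2.1 | 2.3 |
| 430 | as stated | 8.7 | 19.0 | 27.6 | 2.3 | 2.5 |
| 542 | no drop-out | 10.9 | 23.9 | 34.9 | 2.9 | 3.2 |
| 854 | recomputed n | 17.3 | 37.7 | 54.9 | 4.6 | 5.0 |

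**4. How far the rates would have to be wrong.** Ten events per coefficient, used only as a yardstick, means 120 events for 12 coefficients. That is 120/860 = 14.0% overall progression with 430 per group, or 120/802 = 15.0% with 401. With no drop-out it is 120/1,084 = 11.1%. The plan assumes (2.02 + 4.41)/2 = 3.2%.

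**5. Risk that a sparse term separates.** The protocol does not say how many patients will have acute dialysis or repeated AKI, so assume k carriers, each at the AKI group's planned rate. The chance that none has a renal event is (1 − 0.0441)^k: 0.64 for k = 10, 0.41 for k = 20, 0.16 for k = 40. A higher rate among carriers lowers these figures; at twice the rate, k = 20 gives (1 − 0.0882)^20 = 0.16.

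**6. Illustrative simulation.** Covariate prevalences and effects had to be assumed, since the documents give none. The true log hazard ratio was ln 2.21 = 0.79, where 2.21 = ln(1 − p2)/ln(1 − p1). Three sets of runs at about 26–28 events gave:
- at least one coefficient not usefully estimable, or a failed fit, in about 57% and 60% of runs in two sets; in the third, a coefficient other than AKI failed in 38%;
- an unusable AKI estimate or a failed fit in about 8–10% of runs;
- in one set at 430 per group, an SD of the AKI log hazard ratio of 0.54 adjusted against 0.42 unadjusted, with a mean model standard error of 0.46;
- among usable fits, about 95–96% coverage of the 95% interval for AKI, and a mean log hazard ratio of 0.83–0.84 in the two sets that examined bias.

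With about 127 events the share of runs with a non-estimable coefficient fell to about 2%. In 60 runs a Firth-penalised fit always stayed finite, with mean AKI log hazard ratio 0.80 and SD 0.50, against 0.54 for maximum likelihood.

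**The case against.** **The event count is a proxy.** It applies a conversion to renal replacement alone, counts nobody without the early eGFR fall, and has no time horizon. The endpoint is a wider composite followed to ten years (sections 3.1 and 3.2), so events may exceed 26–35. This stands, and the finding is conditional on the planned rates. Step 4 shows how large the excess would have to be.

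**The figure of 401 per group is pessimistic.** Under section 8.3 withdrawn patients count until withdrawal, section 4.3.2 asks them to allow later outcome data, and the renal database identifies chronic renal replacement. This also stands, which is why the range runs up to 35. Excluding controls with later AKI pulls the other way.

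**A covariate that is zero in all controls is not thereby separated.** Correct: separation needs carriers without events (or, rarely, only with events). It is a risk whose size depends on counts the protocol does not give.

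**Partial mitigation exists.** Controls are matched on age and baseline eGFR, and a log-rank comparison is also planned. Fitting details are often left to an SAP. But section 8.2 itself fixes the covariate list, and matching does not shorten it.

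**A stronger reading is tempting:** that the AKI intervals would be unreliable and the hazard ratio badly biased away from the null. Step 6 does not bear this out. Among usable fits coverage was close to nominal, and the mean exceeded the true value by only 0.04–0.05. The adjusted SD above the mean standard error points to extra spread, but is not enough to claim poor coverage.

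**Conclusion.** The point holds for CKD progression. At the rates on which the protocol sizes the study, the fixed model has about 2.1–3.2 events per coefficient, depending on drop-out and on whether race is included. An ordinary maximum-likelihood fit then risks non-estimable sparse terms (acute dialysis, multiple AKI episodes, race), occasional non-convergence and a more variable AKI estimate. The event count is arithmetic on the protocol's own figures. The failure frequencies rest on assumed prevalences and effects and are illustrative only.

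Two wider inferences are not supported. A reader might extend the point to mortality, but the protocol gives no death rate, so nothing can be said either way. A reader might also suppose that correcting the sample size would resolve it, but 854 evaluable patients per group still gives only 4.6–5.0 events per coefficient.

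This is a change that should be made; it does not invalidate the study.

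**What to change.** In section 8.2, add that for CKD progression the adjusted Cox model will be fitted by Firth-penalised partial likelihood with profile-likelihood confidence intervals, keeping the listed covariates. This retains the covariate hazard ratios, which bear on the objective in section 2 of profiling high-risk patients.

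A Cox model with AKI plus one propensity score built from pre-AKI covariates may be added as a sensitivity analysis. The text should then say that it omits acute dialysis, multiple AKI episodes and proteinuria (measured from study entry, about three months after the episode), and that it yields no covariate hazard ratios. Because it adjusts for a different set of variables, it should not replace the main model.

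Cost: one extra modelling step and software beyond a standard Cox routine, so the sentence naming SPSS v19.0 and Stata v11 should be checked and extended if needed. No patients, visits or data are added. The wording is best settled before renal outcomes are analysed. Penalisation does not decide whether covariates arising during or after AKI belong in the model; that is a separate question.

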8.3 Subject Population(s) for Analysis

All patients will be included in the analyses described above except for those in the control group who subsequently sustain AKI during the study period, who will be excluded. Depending on the frequency of this occurrence a separate 'intention to treat' secondary analysis may be performed. Data from patients who withdraw (and give consent) or who die will be included until the date of withdrawal or death.

9 Safety and Adverse Events

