3.1 General Design

This is a long-term longitudinal observational case-control study. Basic blood tests to include measuring renal function, haemoglobin, albumin and proteinuria will be measured at study entry as well as 1 year, 3 years, 5 years and 10 years after AKI (approximately 9months, 33months, 57 months and 117 months after recruitment). Samples will also be collected and stored at each of these time points for subsequent biomarker measurement; these will consist of inflammatory markers (IL-6, high sensitivity CRP) and plus a panel of biomarkers of tubular injury (to include NGAL and IL-18). Included patients will have baseline demographics, co-morbidity and acute illness details extracted from the hospital PAS system. AKI stage and baseline renal function (that prior to sustaining AKI) will be extracted from the electronic AKI reporting system currently in clinical use at the Royal Derby Hospital. This novel system identifies all episodes of AKI from every inpatient location and also reports severity as per AKIN staging; the diagnostic accuracy of this system has been confirmed and reported previously [16].

Patients receiving acute dialysis during the episode of AKI will be identified from renal unit and intensive care unit databases; the renal database (Vitaldata) will be used to identify those patients who subsequently require chronic renal replacement therapy (RRT). The Medical Research Information

Service (MRIS, an arm of the NHS Information Centre) will be used to accurately track survival data of participants to **ten** years after the AKI episode.

A pilot study, specifically designed to test this methodology and recruitment process is currently underway, and demonstrates that the proposed recruitment, consent and matching processes are both practicable and feasible (recruitment rate ~20%, with approximately 15 participants recruited per week).

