3.2 Primary Study Endpoints

- 1. The risk of death in AKI group versus controls.
- 2. The risk of CKD progression in AKI group versus controls.

CKD progression will be defined as doubling of serum creatinine, eGFR<15mls/min or the initiation of renal replacement therapy (dialysis or transplantation).

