4.3 Withdrawal of Subjects

Patients will be withdrawn only if they withdraw their consent.

All patients will be included in the analyses except for those in the control group who subsequently sustain AKI during the study period, who will be excluded.

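### Deleting controls who later develop AKI selects the control group on a post-entry event and can create a difference, chiefly in the unadjusted renal comparison

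*Protocol*

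**What the plan says.** Section 8.3 includes everyone in the analyses of section 8.2 "except for those in the control group who subsequently sustain AKI during the study period, who will be excluded". Section 4.3 states the same rule: "All patients will be included in the analyses except for those in the control group who subsequently sustain AKI during the study period".

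The analyses covered are those of both primary endpoints, death and CKD progression. Section 8.2 says "Kaplan-Meier curves will be constructed to compare the primary endpoints, renal end-point and mortality between the two groups using the Log-Rank test", and then "A Cox proportional hazard model will be used to test the effect of AKI on primary endpoints". It also plans a conditional logistic regression of CKD progression and of mortality status at 12 months.

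The AKI group has no matching exclusion. Patients with further AKI stay in, and the Cox covariates include "requirement for acute dialysis and multiple episodes of AKI".

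The window for exclusion is long. Renal function is "measured at study entry as well as 1 year, 3 years, 5 years and 10 years after AKI" (section 3.1), and survival is tracked to ten years.

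An analysis keeping all controls is mentioned only as an option: "Depending on the frequency of this occurrence a separate 'intention to treat' secondary analysis may be performed".

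**The concern.** Whether a control counts as a control is settled by events over the ten years after entry. A control with AKI in year 8 is removed altogether, including eight AKI-free years and any outcome. An AKI patient with the same second event is kept.

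Two distortions follow. If later AKI marks or causes worse outcome, which is the study's own hypothesis, the rule removes the controls most likely to reach an endpoint and makes index AKI look harmful. It also removes time that a control had to survive in order to reach the later AKI, which makes the retained controls look worse. Nothing makes the two cancel, and they weigh differently on death and on the renal endpoint.

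Read literally, the rule also reaches the 12-month conditional logistic analysis: a control would leave a 12-month comparison because of AKI years afterwards, so that result would change as follow-up continued.

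**Working it through.** **1. Does excluded mean deleted or censored?** Section 8.3 lets patients who withdraw or die contribute until the date of withdrawal or death. It gives controls with later AKI no such date. The natural reading is deletion of the whole patient.

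**2. A null case in closed form.** Suppose index AKI has no effect, so the groups are identical. The assumptions, none of which is in the protocol, are:
- q: ten-year probability of later AKI, 10% to 30%, at a constant rate
- k: multiplier on the endpoint hazard λ after later AKI, 1 to 5
- a rare endpoint, with no competing death

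The share of the ten years spent before later AKI is s = q / (−ln(1−q)). For q = 20%, s = 0.2/0.2231 = 0.896.

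The rate in a complete group is λ[s + k(1−s)]. With all controls kept, both groups have this rate and the ratio is 1.

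With the exclusion there are two cases.

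(a) Later AKI leads to exclusion even when it follows the endpoint. This is the literal rule for the renal endpoint. Retained controls have no AKI in ten years, so their rate is λ, and the ratio is s + k(1−s).

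(b) The endpoint ends the chance of later AKI. This is so for death, and for the renal endpoint if AKI after it is not counted. Over T years, retained controls have λTs expected events in T(1−q) person-years, a rate of λs/(1−q). The ratio is [s + k(1−s)](1−q)/s.

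| q | s | (a) k=2 | (a) k=3 | (a) k=5 | (b) k=1 | (b) k=2 | (b) k=3 | (b) k=5 |
|---|---|---|---|---|---|---|---|---|
| 10% | 0.949 | 1.05 | 1.10 | 1.20 | 0.95 | 1.00 | 1.04 | 1.14 |
| 20% | 0.896 | 1.10 | 1.21 | 1.41 | 0.89 | 0.98 | 1.08 | 1.26 |
| 30% | 0.841 | 1.16 | 1.32 | 1.64 | 0.83 | 0.96 | 1.10 | 1.36 |

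In case (a) the ratio exceeds 1 whenever k exceeds 1. In case (b) the distortions cancel only at k = sq/[(1−q)(1−s)]. For q = 20% that is 0.8963 × 0.2/(0.8 × 0.1037) = 2.16. This is why the renal endpoint is the more exposed.

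**3. Simulation, adding competing death and frailty.** The assumptions were death 5% a year, later AKI 2% to 4% a year, renal hazard multiplied by 3 to 5 and death hazard by 2 after AKI, and frailty SD 0 to 0.7. Between 13% and 26% of controls were excluded. The renal ratio was about 1.1 to 1.8. Mortality was about 0.94 to 1.12, falling to about 0.83 if later AKI carries no excess risk. With all controls kept, ratios were 0.99 to 1.02.

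A wider grid of case (b) type used multipliers 1 to 5 and frailty variance 0 or 1. It ran from 0.82 to 1.98 for a 2% renal risk and from 0.84 to 1.35 for a 30% mortality risk.

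**4. The adjusted Cox model.** Suppose multiple AKI episodes enter as a fixed yes/no covariate that counts later episodes. The group coefficient then compares AKI patients without repeat AKI against controls without later AKI. Under the null these are mirror images, so the ratio is 1. A null simulation gave 0.96 to 1.03 for the renal endpoint and 0.97 to 1.01 for mortality.

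With time-dependent coding and the exclusion still in force, the renal ratio was 0.96 to 1.06 but mortality fell to 0.83 to 0.91. Case (b) agrees: λ divided by λs/(1−q) is (1−q)/s, or 0.83 to 0.95.

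**5. How few events carry the renal result.** Section 8.1 expects 2.02% of 430 controls to progress: 0.0202 × 430 = 8.7, about 9 events. Suppose 43 controls (10%) are excluded and carry 3 of the 9. Control risk falls from 9/430 = 2.09% to 6/387 = 1.55%. With 9 events in 430 AKI patients as well, a true null, the ratio becomes 2.09/1.55 = 1.35.

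**The case against.** The best defence is that the planned Cox model adjusts for multiple AKI episodes. Under one coding this restores symmetry, and under the null the distortion nearly vanishes (step 4). That stands. A reader might infer that a spurious hazard ratio of 1.1 to 1.8 describes the adjusted model; it does not, if the covariate is fixed. The defence is partial, though. The protocol does not define the covariate or its coding. It leaves Kaplan-Meier and log-rank untouched. If index AKI itself raises the risk of later AKI, adjusting for later episodes conditions on a consequence of the exposure.

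A second defence is the optional analysis with all controls. It shows the authors saw the issue, and an analysis plan could set its trigger. It is still secondary and discretionary, so it does not protect the primary result.

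A third is that wanting never-AKI controls is legitimate. It is, but a time-dependent exposure gives that contrast without using the future to choose patients.

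Some stronger readings are not supported:
- **Sample size.** A reader might conclude that the exclusions exceed the drop-out allowance. Section 8.1 allows 26% without saying what it covers. At 20% exclusion, 542 × 0.8 = 434 controls remain before other losses, still above 430.
- **Broken pairs.** Log-rank and Cox are described without pairing, so lost pairs matter only for the conditional logistic analysis.
- **Direction.** A fixed inflation of harm cannot be claimed for mortality, which moves either way.

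**Conclusion.** The point holds. The rule is stated twice, applies to one group and covers both primary endpoints. That it selects controls on a post-entry event follows from its structure; only the size is uncertain.

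For the unadjusted comparisons under the null, the renal ratio is about 1.1 to 1.8 if later AKI raises renal risk. It can be near or below 1 if the multiplier is about 2 or less, frailty is absent and AKI after the renal endpoint is not counted. Mortality is about 0.84 to 1.12, with higher values only under strong shared frailty and large multipliers. All these figures rest on assumed rates and take no account of the planned adjustment for age, co-morbidity and renal function, which would absorb some of the frailty. The adjusted Cox estimate may be nearly unaffected or may be distorted, depending on a coding choice that the protocol leaves open.

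A reader might infer that keeping all controls gives an unbiased comparison. It removes this selection only. The study remains observational, and confounding is not addressed by the change.

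**What to change.** Amend sections 4.3 and 8.3 together:
- The primary analysis compares groups by AKI status at the index admission, with every control kept for full follow-up, including in the 12-month analysis.
- A prespecified secondary model treats later AKI as a time-dependent exposure, in the same way in both groups, using episodes found by the electronic reporting system.
- Later episodes are not used as a fixed baseline covariate in the primary Cox model. Section 8.2 should say which episodes the multiple-episode covariate counts.
- The analysis excluding controls with later AKI is kept only as a sensitivity analysis.

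The cost is mainly protocol wording. Section 4.4 lists data from the index admission only, so dates of later AKI should be added, although the existing rule already requires these patients to be identified. There are two downsides. The primary contrast is diluted somewhat toward the null compared with never-AKI controls, which the time-dependent model addresses. Later AKI treated at other hospitals may be missed, which weakens that secondary model but not the primary comparison.
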